The power $(1 - \beta)$ of a study design is the probability that a specified difference between populations will be detected if it in fact exists. In general, power is a direct function of sample size; that is, for a particular study design, the more subjects measured the larger the study power. It is understood that these analyses make use of the entire known RANCH HAND population (and exclude ancillary exposed groups for reasons previously cited); the exposed sample size cannot be increased. Power augmentation, therefore, can only be accomplished by the less efficient procedure of increasing the control group size which has statistical limitations as well as staggering financial and logistic considerations. Hence, considerable effort has been made to correct loss to study issues (by replacement and other techniques to induce participation) and to use the most powerful statistical design concepts. Essentially all previous animal and human studies concerning herbicide suffer from a lack of adequate consideration of study power. The following presents a preliminary analysis of study power for the case of continuous and dichotomous variables expected from the study.

(1) Power in Continuous Variable Case

Assume that blood cholesterol levels are being compared between RANCH HAND and control groups, and that the coefficient of variation for cholesterol in the control group is 0.1, where the coefficient of variation is the ratio σ_c/μ_c . Assume $\sigma_{RH} = \sigma_c$. The symbol α is the probability that the study will indicate an effect where none exists, and $1-\beta$ is the power as defined before. Consider that the RANCH HAND mean cholesterol μ_{RH} is shifted from the control mean μ_c . A natural question is to inquire about the study power as a function of available pairs (n) and mean ratio $\gamma = \mu_{RH}/\mu_c$.

TABLE 11

POWER CALCULATIONS

ASSUMPTIONS: $\alpha=0.05$, $\sigma_c/\mu_c=0.1$, $\gamma=\mu_{RH}/\mu_c$

r	γ	Power = 1-β	
		n=180	n=450
.20	1.01	.20	.38
.20	1.02	.55	.88
.20	1.05	>.995	>.995
.70	1.01	.86	.995
.70	1.02	>.995	>.995
.70	1.05	>.995	>.995

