Power calculations are displayed in Table 11. Study power in the case of a matched pair design is strongly dependent on the degree of positive correlation produced between the involved groups by the matching procedure. Of course, the degree of correlation can be expressed by the correlation coefficient r which can take values between -1 (negative correlation) and + 1 (positive correlation), and two values of r have been employed in Table 11. From this table it is seen that if only 450 pairs are studied a 1% shift in mean (= 1.01) will not be reliably detected, but a 2% shift will be detected with a probability of 0.88 if r = 0.2 at least. From this calculation one can infer the need to examine at least 450 pairs to obtain the 2% shift, and to strive for more if possible.

(2) Power in the Dichotomous Variable Case. There is significant discussion in the mathematical statistics literature concerning the efficacy of paired designs in the setting of dichotomous responses (Billewicz, 1974; Ury, 1975; Miettinen, 1970; and several others). Table 12 shows a set of calculations which are applicable to the present study.

TABLE 12

POWER CALCULATIONS FOR THE DICHOTOMOUS VARIABLE CASE AS A
FUNCTION OF EFFICACY OF PAIRED DESIGNS

				POWER = 1 - β		
P_1	P_2	Rel. Risk	r	n=250	n=350	n=450
.05	.01	5	0	.77	.82	.92
.04	.01	4	0	.61	.75	.85
.03	.01	3	0	.40	.51	.59
.10	.05	2	0	.61	.75	.85
.20	.10	2	0	.87	.94	.97
*						
.05	.01	5	.1	.89/.029	.94/.032	.98/.064
.04	.01	4	.1	.72/.033	.87/.038	.88/.041
.03	.01	3	.1	.38/.020	.68/.046	.71/.077
.10	.05	2	.1	.76/.055	.85/.048	.88/.048
.20	.10	2	.1	.94/.043	.98/.046	.99/.057
**						

* $\alpha = .050$ **** α as indicated

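### Table 11: three of the six power values printed under r = .70 do not follow from the table's stated assumptions; they fit r of about .90

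*Protocol*

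**What the plan says.** Section VI.F(1) of the Protocol works through blood cholesterol as an example. It supposes that the "coefficient of variation for cholesterol in the control group is 0.1", takes the two groups' standard deviations as equal, and sets alpha to .05. Alpha is described only as what "is the probability that the study will indicate an effect where none exists", so sidedness is not stated. The aim is put this way: "A natural question is to inquire about the study power as a function of available pairs (n) and mean ratio". The Executive Summary names a paired difference statistic for continuous variables.

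Table 11 gives power for 180 and 450 pairs at mean ratios 1.01, 1.02 and 1.05. The text introduces the role of r with the statement "Study power in the case of a matched pair design is strongly dependent on the degree of positive correlation produced" by matching. It notes that "two values of r have been employed in Table 11" but does not name the second value, so .70 appears only in the table. The printed powers (180 pairs / 450 pairs) are:

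- r = .20: .20/.38 for a 1% shift, .55/.88 for 2%, >.995 in both columns for 5%.
- r = .70: .86/.995 for 1%, >.995 in both columns for 2% and for 5%.

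The text then says that with 450 pairs a 1% shift will not be detected reliably, "but a 2% shift will be detected with a probability of 0.88" if r is at least 0.2. From this it concludes that at least 450 pairs should be examined.

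**The concern.** In a paired comparison with fixed SD, shift and number of pairs, r affects power only through the SD of the within-pair difference. The r = .20 rows therefore determine what the r = .70 rows must be. The printed jump for a 1% shift with 180 pairs, from .20 to .86, is larger than a change in r from .20 to .70 can produce.

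At stake is how much protection matching gives. As printed, matching at r = .70 makes a 1% shift detectable at .86 with only 180 pairs, which suggests that well-matched continuous endpoints tolerate heavy loss to study. On the stated assumptions, 450 pairs at that r fall just short of .80, the minimum target named in Section VI.F(2). A reader relying on the table could put too much weight on a null result for a small mean shift.

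**Working it through.** **Inputs.** From Section VI.F(1) and Table 11: alpha .05; SD = 0.1 of the control mean in both groups; shift d = .01, .02 or .05 of the control mean; n = 180 or 450 pairs; r = .20 or .70. From the Executive Summary: a paired difference test. Assumption: two-sided testing, because it fits the r = .20 rows (shown below).

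**Formulas.** SD of a paired difference = 0.1 × √(2(1 − r)). Noncentrality δ = d√n / SD of difference. Power = Φ(δ − 1.96). The noncentral t gives the same results to within half a percentage point.

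**Step 1: reproduce the r = .20 rows.** SD of difference = 0.1 × √1.6 = .1265.

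| Shift | n | δ | Two-sided power | Printed |
|---|---|---|---|---|
| 1% | 180 | 1.06 | .184 | .20 |
| 1% | 450 | 1.68 | .389 | .38 |
| 2% | 180 | 2.12 | .564 | .55 |
| 2% | 450 | 3.35 | .918 | .88 |
| 5% | 180 and 450 | – | >.995 | >.995 |

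All cells agree within two points except .88, which is about four points low. One-sided testing gives .28/.51 for 1% and .68/.96 for 2%, which does not fit. The table was therefore computed two-sided, or close to it.

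**Step 2: same formula at r = .70.** SD of difference = 0.1 × √0.6 = .0775.

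| Shift | n | δ | Two-sided power | One-sided power | Printed |
|---|---|---|---|---|---|
| 1% | 180 | 1.73 | .410 | .535 | .86 |
| 1% | 450 | 2.74 | .782 | .863 | .995 |
| 2% | 180 | 3.46 | .934 | .966 | >.995 |
| 2% | 450 | 5.48 | >.995 | >.995 | >.995 |
| 5% | 180 and 450 | – | >.995 | >.995 | >.995 |

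Three cells fail and three hold. For the 1% shift the printed values are 45 and 21 points too high (.86 − .41 and .995 − .78). One-sided testing does not recover any of the three failing cells.

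**Step 3: a check that does not use the SD.** For the same shift and n, δ at r = .70 divided by δ at r = .20 must be √(.8/.3) = 1.63, whatever the coefficient of variation. The printed two-sided powers imply:

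- n = 180: (1.960 + 1.080)/(1.960 − 0.842) = 3.040/1.118 = 2.72.
- n = 450: (1.960 + 2.576)/(1.960 − 0.305) = 4.536/1.655 = 2.74.

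A different coefficient of variation therefore cannot reconcile the two blocks. Solving .8/(1 − r) = 2.72² or 2.74² gives r of about .89 in both columns.

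**Step 4: what r fits the printed block?** Starting from a coefficient of variation of 0.1, .86 implies r = .903 and .995 implies r = .891. At r = .90 the SD of the difference is 0.1 × √0.2 = .0447, which gives .851 and .997 for the 1% shift and >.995 for the 2% and 5% shifts. All six printed cells are then matched closely.

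**Step 5: other forms of the SD.** 0.1√(1 − r), 0.1√2(1 − r), 0.1√(2(1 − r²)), 0.1√(1 − r²) and 0.1(1 − r) were tried. None gives .86/.995. The nearest, 0.1√2(1 − r), gives .885/.999 and misfits r = .20 (.66 against the printed .55 for 2% at n = 180). Letting the exposed SD be 1.01 times the control SD gives .41/.78 again.

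**Step 6: pairs needed at r = .70 for a 1% shift and power .80.** n = .006 × ((1.960 + 0.842)/.01)² ≈ 471 by the normal formula, or about 473 with the t distribution.

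**The case against.** The strongest reply is that the powers may be right and the label wrong. The whole block fits r = .90 about as well as the upper block fits r = .20, and nothing in the running text confirms .70. The label could be a typing error, or a misreading of an old typescript, although it would have to recur in three rows. This stands: the documents do not show which of the two is wrong, so it cannot be said that .86 must become .41.

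The second reply is that nothing in the plan turns on these cells. This also largely stands. A reader might infer that the sample-size conclusion collapses or that the study is underpowered for continuous endpoints. The documents do not support that. The only conclusion drawn, on 450 pairs and a 2% shift, comes from the r = .20 row, where the true power is higher than printed. The exposed group cannot be enlarged, no subsampling is planned, and the text repeatedly urges examining as many pairs as possible. The preference for continuous measurements (Sections V.D(4) and VIII.H) rests on a general comparison with dichotomous data and cites neither r = .70 nor a 1% shift.

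A reader might also infer that the whole r = .70 block is wrong, but half of its cells are correct as printed. Nor is the .78 far from target. The expected 40% examination attendance gives 480 pairs from 1200 men (power .81 at r = .70 for a 1% shift) or 400 pairs from the 1000 assumed in Section VI.B(1) (power .73), if every attender is paired. That straddles .80.

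The reply does not remove the inconsistency. Label and powers cannot both be right, and calling the analysis preliminary does not change that.

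**Conclusion.** The point holds for three cells of Table 11: r = .70 with a 1% shift at both sample sizes, and with a 2% shift at 180 pairs. On the stated inputs they should read .41, .78 and .93, where the table prints .86, .995 and >.995. Either these powers or the r label is wrong. As labelled, the table overstates what matching gains for small shifts.

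The .88 at r = .20 (2% shift, 450 pairs) should be .92. This is minor and errs on the cautious side.

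The result rests on two-sided testing, which the protocol does not state but its r = .20 rows imply, and on the unadjusted paired difference. The cells fail under one-sided testing as well. Because no design choice or stated conclusion depends on them, this is a moderate correction and not one on which the plan stands or falls.

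**What to change.** Check the original calculation, or the printed page, for the r used in the lower block of Table 11. Then do one of the following:

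- If r was .90, relabel the three rows r = .90. The printed powers can stay.
- If r was .70, replace .86, .995 and the >.995 for a 2% shift at 180 pairs with .41, .78 and .93. Leave the other three cells. Add that a 1% shift at r = .70 needs about 471 to 473 pairs for power .80.

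In either case, change .88 to .92 in the table and in the sentence of Section VI.F(1) that repeats it, and state that the test is two-sided. The cost is one label or three cells, plus one further cell and one or two sentences. No procedure, sample size or analysis changes.

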Since this study is dealing with unknown clinical endpoints, determination of a disease state by statistical methodology is a prime thrust of the investigation. Inferences about a disease state will be developed by identifying symptom complexes or physical findings which in themselves may represent disease. By comparison of symptoms, signs and laboratory tests within and between groups, a logical decision-making scheme can be utilized to calculate relative risks from baseline data. If appropriate, these results will be used to sharpen adaptive approaches in the follow-up study. By the use of combinational and correlational analysis, statements about the probability of a disease state, a subclinical state, and/or over-reporting bias will be attempted. In addition, the application of regression techniques to a normalized exposure index among exposed individuals exhibiting symptoms and/or signs will also assist in the determination of a disease state. Beyond these pair-wise and group comparisons, newer techniques of pattern recognition, such as Factor Analysis and Cluster Theory, are being considered in order to achieve a more automatic and objective analysis. Mortality data will be analyzed using several different approaches, including age and age-disease specific rates, standardized mortality rates and modified life table approaches, as well as more sophisticated logistic and multiplicative models (survival analysis). Analysis of questionnaire and physical examination data will utilize log-linear models to verify the appropriateness of the standard statistical methodologies (e.g., McNemar's test for dichotomous rates). Polytomous or categorical findings will be analyzed by the use of log-linear models. Continuous variables will undergo covariance analysis to remove non-controlled effects, followed by the use of a paired difference statistic. Some data will naturally fall into groups (e.g., fertility/reproduction, liver function tests) in which case, multiway contingency table analysis or extensions of the generalized linear model analyses will be used.

PROJECT RANCH HAND II

EPIDEMIOLOGIC INVESTIGATION OF HEALTH EFFECTS
IN AIR FORCE PERSONNEL FOLLOWING EXPOSURE TO HERBICIDE ORANGE

MATCHED COHORT DESIGN

I. Purpose of the Investigation

The purpose of this investigation is to determine whether long-term health effects exist and can be attributed to occupational exposure to Herbicide Orange through the use of epidemiologic techniques.

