Operation RANCH HAND personnel flew C-123 aircraft in RVN during 1962-1970. Data from hand-compiled lists obtained through the RANCH HAND Association (a reunion organization), Air Force personnel computer entries, historical records and actual C-123 flight orders, place the estimated study population at approximately 1200 individuals. Of those personnel confirmed by the USAF computer system, 25% are still on active duty, with the remainder being composed of retired or separated persons. An indepth search to identify all RANCH HAND participants is being conducted of all organizational records stored at the Military Records Division, National Personnel Records Center (NPRC), St. Louis, Missouri. Detailed advertisements in active/retired military trade journals, VA publications, and local newspapers may be pursued in the near future to insure maximal ascertainment/identification of the exposed group. Introductory letters will be sent to the last known address of all identified persons, and nonresponse will be pursued by cross-locator systems available within the government (e.g., Social Security Administration, VA, Internal Revenue Service). Significant efforts will be made to account for at least 99% of the total population (see Figure A-2, Section XII). Because of the limited number of estimated RANCH HAND personnel (1200), no subsampling of the exposed group is planned in any phase of the study. All members will be strongly encouraged to participate in all phases of the investigation.

(a) Known or Predicted Characteristics of the Exposed Group

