In this figure, r is again the correlation coefficient indicating the degree of correlation induced between the involved groups by the matching procedure. The probability of the disease among RANCH HAND personnel is symbolized as p_1 , while p_2 is the probability of the disease among the controls. Relative risk is the ratio p_1/p_2 . With $r = 0.1$, sign test power tables were used as an exact version of McNemar's test, and therefore different α levels are shown under each power number. Table 12 shows the positive influence of effective pairing in the higher power levels noted. For example, it appears that for $p_2 = 0.01$ and $p_1 = 0.03$, physical examination of 450 pairs (900 examinations) will disclose the three-fold relative risk with probability less than the minimum target .80. In other words, there is a greater than "20% chance" that a three-fold relative risk on a 1/100 disease state will go undetected in this study if only 350 pairs are examined and if low correlations occur. Once again the need to examine the maximum numbers of pairs in the study is seen.

To present these dichotomous power calculations more clearly, calculations in the context of actual disease states have been accomplished. The diseases considered are cardiovascular disease and cancer, corresponding to high and low rate illnesses for the age groups presently under investigation.

Cardiovascular Disease. A logistic risk function was fitted to data from 17,455 autopsies gathered in a WHO collaborative study in Czechoslovakia, Sweden and the USSR. The function fitted has the form

$$P = [1 + \exp(\alpha + \beta(x-.5) + \gamma(y-.5))]^{-1}$$

where

p = the probability of a complicated coronary lesion

x = age scaled linearly so that x = 0 is equivalent to 3 years, and x = 1 is equivalent to 58 years (the age span of the current study)

y = 1 or 0 if the subject is exposed or not

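### Table 11 does not reproduce from its own stated assumptions, and the inference that at least 450 pairs are needed for a 2% shift does not follow from it

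*Protocol*

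**What the plan says.** Section VI.F(1) of the protocol works through a cholesterol example. It assumes that "the coefficient of variation for cholesterol in the control group is 0.1", that both groups have the same SD, and that alpha is 0.05. Table 11 gives power at two numbers of pairs, 180 and 450, for mean shifts of 1%, 2% and 5%. On the within-pair correlation, the text notes that "two values of r have been employed in Table 11"; these are .20 and .70. From the table it reads that "a 2% shift will be detected with a probability of 0.88 if r = 0.2 at least", and then draws its conclusion: "From this calculation one can infer the need to examine at least 450 pairs to obtain the 2% shift". It adds that more pairs should be sought if possible.

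The paragraph names no target power. The only explicit target nearby is in Section VI.F(2), on dichotomous outcomes, where 450 pairs are said to detect a three-fold risk "with probability less than the minimum target .80". The cancer example later in that subsection is also sized for 0.80.

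The Executive Summary says continuous variables will have covariance analysis, "followed by the use of a paired difference statistic". Section V.B(1) says that "no subsampling of the exposed group is planned in any phase of the study".

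**The concern.** Table 11 is the protocol's only power statement for continuous outcomes, and Section VIII.H relies on such outcomes to offset weak power elsewhere. Section V.F(2) ties the strength of any inference to the power of the study. If the table is wrong, a negative result on a continuous measure will be read against the wrong power.

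Two things look wrong. First, the stated inputs fix every cell of the table, so each can be checked, and the .88 on which the text rests its conclusion looks too low. Second, two columns can show that 180 pairs are too few and 450 are enough. They cannot show that nothing between them would do, and a minimum has no meaning until a target power and a correlation are named.

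**Working it through.** **Inputs.** From Section VI.F(1) and Table 11: SD/mean = 0.1 in both groups; shift d = .01 or .02 of the mean; r = .20 or .70; n = 180 or 450 pairs; alpha = .05. Sidedness is not stated. Two-sided is used because it fits three of the four unsaturated r = .20 cells, and one-sided does not (it gives .280, .513 and .683 where .20, .38 and .55 are printed). The analysis is a paired difference, as in the Executive Summary.

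**Formulas.**

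- SD of the paired difference, relative to the mean: s = 0.1 × √(2(1 − r)). This is .1265 at r = .20 and .0775 at r = .70.
- Power = Φ(d√n / s − 1.96).
- Pairs needed = 2(1 − r) × [0.1 × (1.96 + z_power) / d]².

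**Step 1: reproduce the table.**

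| r | Shift | Pairs | Printed | Recomputed |
|---|---|---|---|---|
| .20 | 1% | 180 | .20 | .184 |
| .20 | 1% | 450 | .38 | .389 |
| .20 | 2% | 180 | .55 | .564 |
| .20 | 2% | 450 | **.88** | **.918** |
| .70 | 1% | 180 | **.86** | **.410** |
| .70 | 1% | 450 | **.995** | **.782** |
| .70 | 2% | 180 | **>.995** | **.934** |

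The remaining cells, all printed as >.995, reproduce. For the .88 cell the calculation is .02 × √450 / .1265 = 3.354, then 3.354 − 1.96 = 1.394, and Φ(1.394) = .918.

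**Step 2: try other readings of the .88 cell.** A t test gives .917. Letting the exposed SD grow with its mean gives .913. A one-sided test gives .956. None gives .88. A correlation of about .10 would (.885), but the row is labelled .20.

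**Step 3: try another correlation for the r = .70 rows.** At r = .90, s = 0.1 × √0.2 = .0447. A 1% shift then has Φ(3.00 − 1.96) = .85 at 180 pairs and Φ(4.74 − 1.96) = .997 at 450. A 2% shift at 180 pairs has Φ(6.00 − 1.96), which is above .995. These roughly match the printed entries, so the rows may have been run at, or may be meant to be labelled, about .90.

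**Step 4: pairs needed for a 2% shift, two-sided alpha .05.**

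| Target power | r = .20 | r = .10 | r = 0 |
|---|---|---|---|
| .80 | 314.0 | 353.2 | 392.4 |
| .85 | 359.1 | 404.0 | 448.9 |
| .88 | 393.1 | 442.3 | 491.4 |
| .90 | 420.3 | 472.8 | 525.4 |

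For example, at r = .20 and power .80: 1.6 × [0.1 × 2.8016 / .02]² = 1.6 × 196.2 = 314. At r = .20 the stated 450 exceeds the need by 43% at .80, 25% at .85, 14% at .88 and 7% at .90. It matches the need only at a target of about .918 (449 pairs).

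**Step 5: the same check from the printed powers alone.** Scaling by n × [2.8016 / (1.96 + z_power)]² gives the pairs for .80. From .55 at 180 pairs this is 180 × (2.8016 / 2.0857)² ≈ 325. From .88 at 450 pairs it is 450 × (2.8016 / 3.135)² ≈ 359. So even the printed figures do not make 450 the minimum for .80.

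**The case against.** The strongest reply is that the number 450 does no work in the design. It is one of two tabulated scenarios in an example the protocol calls preliminary. The whole exposed group is invited, and Sections VI.F(1) and VI.F(2) both urge as many pairs as possible. With about 40% expected at examination (Section VIII.G), a population of 1200 would yield about 480 and one of 1000 about 400, so 450 is close to the likely yield anyway. Table 12 shows that 450 pairs reach only .59 (r = 0) or .71 (r = .1) for a three-fold risk on a 1-in-100 condition, so 450 is not excessive for the examination as a whole. The .88 entry also errs on the cautious side. All of this stands.

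It also rules out a stronger reading that a reader might infer: that 450 is a required sample over 40% too high, and that a study ending with fewer pairs would be judged a failure. The 43% excess holds only if .80 is the target, and that target is stated in the dichotomous subsection. The challenged sentence follows a power of 0.88, where the excess is 14%. No section makes 450 pairs a criterion of successful recruitment.

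The reply does not rescue the table. Four cells disagree with their own inputs, and the three at r = .70 err in the optimistic direction. Nor does it show how two columns yield a minimum.

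**Conclusion.** The point holds as an error in stated power and an inference that does not follow. It is not an oversized sample.

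- The .88 entry, in the table and repeated in the text, is about 4 points too low; it should be about .92.
- At r = .70 the 1% entries are too high by about 45 points (180 pairs) and 21 points (450 pairs), and the 2% entry at 180 pairs by about 6 points.
- At r = .20 the pairs needed for a 2% shift run from about 314 to 420 as the target goes from .80 to .90. With no matching correlation, about 393 pairs give .80.

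This rests on a paired-difference test, equal SDs, a coefficient of variation of 0.1 and two-sided alpha of .05; the sidedness is inferred from the cells that fit. If the r = .70 rows were run at about r = .90, their label is wrong instead of their values, but that cannot be settled from the document. The consequence lies in how a negative continuous-variable result is interpreted: the r = .70 rows promise sensitivity to a 1% shift that the stated inputs do not give.

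**What to change.** 1. Replace .88 with .92 in Table 11 and in the sentence that repeats it.
2. Recompute the r = .70 rows (.41 and .78 for a 1% shift; .93 for a 2% shift at 180 pairs), or correct the r label if the runs used another correlation. State whether alpha is two-sided.
3. Replace the sentence calling for at least 450 pairs with the pairs needed by target power and r. For a 2% shift: about 314 for .80, 359 for .85, 393 for .88 and 420 for .90 at r = .20, and about 393 for .80 at r = 0.
4. Keep the instruction to examine as many pairs as possible, and attribute it to the dichotomous outcomes, which need it.

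The cost is up to four table entries (or a row label plus the .88 entry), a note on sidedness and a rewording of the accompanying text. Enrolment, matching, replacement and analysis are unchanged.

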and where $\alpha_1, \beta_i, i=1,2,\dots$ are coefficients to be estimated from the data. Testing for a group difference can be accomplished by estimating β_4 and interaction coefficients such as β_5 . If all interaction coefficients involving the exposure variable E are zero and E is treated as a 0/1 variable, Cox (1958a, 1958b) has shown that the most powerful test for non-zero β_4 , in the setting of matched pairs, is McNemar's test. This latter test makes full use of the paired design of the study. For McNemar's test, the data are cast into a 2 x 2 table as shown in Table 8. In this table, "a" is the number of pairs in which both members have died, "b" is the number of pairs in which only the RANCH HAND person has died, etc. Using McNemar's test, the test statistic

$$\chi^2 = \frac{|b - c|^2}{b + c}$$

is calculated and referred to the chi-square distribution with one degree of freedom. Cox (1966) and Meittinen (1969) provide extensions of McNemar's test for R controls per exposed (R-to-1 matching). Of course the above analyses will be accomplished considering all deaths, and deaths by specific cause.

TABLE 8
FORMAT OF McNEMAR'S TEST
CONTROLS

RANCH HAND PERSONNEL	DEAD	ALIVE	TOTAL
Dead	a	b	a+b
Alive	c	d	c+d
Total	a+c	b+d	n

As discussed in section V above, RANCH HAND personnel may be characterized as risk takers. This risk taking behavior may be associated with increased mortality from a variety of causes. If herbicide exposure has caused neuropathy in the RANCH HAND personnel, one could anticipate that this disability would increase the probability

of accidental death. Therefore, accidental death rates among RANCH HAND participants will be corrected for risk taking. This can be accomplished by including assessment of risk taking behavior in the questionnaire, indepth interview and psychological evaluation. Both control and RANCH HAND mortality could be corrected using these measures, with the resultant rates being less biased and, therefore, a better indicator of exposed versus control effect.

D. Analysis of Questionnaire and Physical Examination Data

The Questionnaire and Physical Examination will produce data of three types: (1) dichotomous, (2) polytomous and (3) continuous.

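### Table 12's paired (r = .1) panel appears to use one-tailed alpha at 250 and 350 pairs but two-tailed alpha at 450, so most of the apparent gain from pairing at 250 and 350 pairs is an artefact

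*Protocol*

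**What the plan says.** Section VI.F(2), Table 12, gives power for five pairs of event rates at 250, 350 and 450 pairs. The upper panel (r = 0) is footnoted as alpha .050. The lower panel (r = .1) prints power and alpha together and is footnoted "α as indicated". Of the correlation, the text says that "r is again the correlation coefficient indicating the degree of correlation induced between the involved groups by the matching procedure".

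The only explanation for the varying alphas is that "sign test power tables were used as an exact version of" McNemar's test, which is why each power comes with its own alpha. Neither the table nor the text says whether any alpha is one- or two-tailed.

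The text then concludes that "Table 12 shows the positive influence of effective pairing in the higher power levels noted". It judges a worked example (.03 vs .01) against a minimum target power of .80.

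The McNemar statistic planned in Section VI.C, and carried over to dichotomous findings in Section VI.D, "is calculated and referred to the chi-square distribution with one degree of freedom". That is a two-sided test.

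**The concern.** Two features of the r = .1 panel are odd. Power hardly rises from 350 to 450 pairs in two rows (.87 to .88 for .04 vs .01; .68 to .71 for .03 vs .01), although it climbs steadily in the r = 0 panel. The gain credited to a correlation of only .1 is also large: .68 against .51 for .03 vs .01 at 350 pairs, and .76 against .61 for .10 vs .05 at 250.

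A change of tail between columns and between panels would explain both. If so, the table cannot support the statement about pairing, and some cells shown above the .80 target are below it for the test that will be used.

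**Working it through.** **Inputs.** Rates, r, n and printed power/alpha are from Table 12. The two-sided test is from Section VI.C.

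**Step 1: set up the pairs.** With q = 1 − p:
- p11 = p1·p2 + r·√(p1·q1·p2·q2), b = p1 − p11, c = p2 − p11
- expected discordant pairs m = n(b + c), and θ = b/(b + c)

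Example, .04 vs .01: p11 = .0004 + .1 × .0195 = .00235, so b = .03765, c = .00765, b + c = .0453, θ = .831. At n = 350, m = 15.9, or about 16.

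**Step 2: reproduce the printed panel.** For m near its expected value, find the rule (k or more of m in one direction) whose binomial tail at ½ gives the printed alpha. Then compute its power at θ. Each cell shows the rule, recovered alpha and power, with the printed power/alpha in brackets.

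| Rates | n = 250, one tail | n = 350, one tail | n = 450, two tails |
|---|---|---|---|
| .05/.01 | 11 of 14: .0287, .893 (.89/.029) | 14 of 19: .0318, .967 (.94/.032) | 17 of 24: .0639, .990 (.98/.064) |
| .04/.01 | 9 of 11: .0327, .720 (.72/.033) | 12 of 16: .0384, .882 (.87/.038) | 15 of 20: .0414, .893 (.88/.041) |
| .03/.01 | 8 of 9: .0195, .372 (.38/.020) | 10 of 13: .0461, .677 (.68/.046) | 12 of 16: .0768, .727 (.71/.077) |
| .10/.05 | 21 of 32: .0551, .760 (.76/.055) | 28 of 44: .0481, .850 (.85/.048) | 37 of 58: .0479, .868 (.88/.048) |
| .20/.10 | 36 of 58: .0435, .950 (.94/.043) | 48 of 80: .0465, .988 (.98/.046) | 60 of 100: .0569, .994 (.99/.057) |

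Power agrees within 2 points in 14 of 15 cells; the other (.94 against .967) is 2.7 points off. The clearest evidence is a single rule, 12 or more of 16. It is printed as .038 for .04 vs .01 at n = 350 and as .077 for .03 vs .01 at n = 450, and 2 × .0384 = .0768. For .10 vs .05 at n = 350, a two-tailed rule (29 of 44) also gives an alpha near .049, but its power would be .765; only the one-tailed rule gives the printed .85.

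The last row is weaker evidence, because with m this large other rules come close. At n = 450, 60 of 103 one-tailed gives .0572, so that cell cannot be assigned uniquely.

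**Step 3: the r = 0 panel.** A two-sided .05 arcsine calculation with interpolated effect size reproduces 14 of 15 cells within 2 points (exception: .05 vs .01 at n = 350, .87 against the printed .82). One-sided, it reproduces 1 of 15.

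**Step 4: recompute r = .1 at two-sided .05.** Two methods:
- Normal: power = Φ{[√n(b − c) − 1.96√(b + c)] / √[(b + c) − (b − c)²]}
- Exact unconditional: average the exact two-sided sign-test power over the binomial distribution of the discordant count

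Example, .04 vs .01, n = 350: [18.71 × .03 − 1.96 × .2128] / √(.0453 − .0009) = .144/.211 = .68, and Φ(.68) = .75. Exact: .72.

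| Rates | n = 250: stated → normal/exact | n = 350 | n = 450 |
|---|---|---|---|
| .05/.01 | .89 → .78/.75 | .94 → .90/.90 | .98 → .96/.96 |
| .04/.01 | .72 → .61/.52 | .87 → .75/.72 | .88 → .85/.84 |
| .03/.01 | .38 → .38/.26 | .68 → .50/.41 | .71 → .61/.54 |
| .10/.05 | .76 → .60/.54 | .85 → .75/.72 | .88 → .85/.83 |
| .20/.10 | .94 → .91/.90 | .98 → .97/.97 | .99 → .99/.99 |

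**Step 5: the gain from pairing at equal alpha.** Going from r = 0 to r = .1 by the same method and the same two-sided .05 adds about 0.5 to 4.5 points across the cells. By the normal formula, .04 vs .01 at n = 350 goes from .72 to .75, and .10 vs .05 at n = 250 from .56 to .60. The table's largest gain is .68 − .51 = .17.

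**Step 6: pairs needed for .80 with r = .1.** Roughly 400 (normal) to 420 (exact) for both .04 vs .01 and .10 vs .05.

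**The case against.** The strongest reply is that nothing in the design rests on these cells. Section VI.F calls the analysis preliminary and says that the exposed group cannot be enlarged. The 450-pair minimum comes from Table 11. The worked example already concludes that power is below .80, Section VIII.H concedes low power for uncommon conditions, and the protocol openly prints a different alpha in each cell. At 450 pairs, .04 vs .01 and .10 vs .05 still exceed .80 after correction. All of this stands, and it limits the consequence. It does not make the table right: a reader can see that alpha varies, but not that its meaning changes between columns.

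Four stronger readings are tempting, and the document does not support them.
- **Every r = .1 cell is overstated.** .03 vs .01 at n = 250 is unchanged by the normal approximation, and .20 vs .10 at n = 350 and 450 hardly moves. At n = 450 the excess for .05 vs .01 and .03 vs .01 comes from printed alphas of .064 and .077, which are visible.
- **Pairing gains nothing.** A small real gain remains, and the protocol's own cardiovascular example calls the benefit slight.
- **Working at the expected discordant count inflates power further.** The direction varies by cell. At two-sided alpha of at most .05, power at the expected count is below the averaged power for .04 vs .01 at n = 250 (.42 against .52) and above it for .03 vs .01 at n = 250 (.37 against .26).
- **Recomputing the r = .1 panel alone is enough.** Exact paired values beside the printed r = 0 values would make pairing appear to lose power (.26 against .40 for .03 vs .01 at n = 250), because the two panels came from different methods.

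**Conclusion.** The stated powers are wrong as written. The r = .1 panel mixes one-tailed alpha (250 and 350 pairs) with two-tailed alpha (450 pairs) and is set beside a two-sided r = 0 panel. Most of the apparent pairing gain at 250 and 350 pairs is therefore an artefact. For the two-sided test planned, .04 vs .01 and .10 vs .05 at 350 pairs, and .05 vs .01 at 250, fall from above the .80 target to between .72 and .78. At 450 pairs, .03 vs .01 is .54 to .61, against .71.

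The tails are inferred from the printed alphas, since the protocol does not state them. The inference is firm for the lower-rate rows and weak for .20 vs .10. The recomputed powers assume r = .1 as defined above.

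The affected range is a realistic one. Section V.D(2) expects 40% examination participation, which gives 480 pairs from the 1200 men of Section V.B(1) or 400 from the approximately 1000 of Section VI.B(1). At 400 pairs both scenarios sit at about .78 to .81. The advice to examine as many pairs as possible stands.

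**What to change.** - Recompute both panels of Table 12 by one named method at one stated two-sided alpha of .05, and print that alpha once.
- Replace the sentence on pairing with one saying that r = .1 adds only about 0 to 5 points at equal alpha.
- State that a four-fold risk on 1/100 and a two-fold risk on 5/100 need roughly 400 to 420 pairs for power .80.
- In the worked example, reconcile the sentence that refers to 450 pairs with the next one, which refers to 350.

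The cost is one recalculated table and a few edited sentences. Stated power becomes less favourable in most cells of the paired panel; sample, matching and conduct do not change.
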